### ***6.1.1 Analyses in Support of Primary Efficacy***

Non-responder imputation analyses that assess the EASI-75 and EASI-90, i.e., proportion of moderate-to-severe atopic dermatitis patients achieving a 75% (or 90%) reduction in the EASI, will also be conducted. P-values from Fisher's exact test may be used due to the potential for low response rates.

Observed cases analyses of EASI-50, EASI-75 and EASI-90 will also be conducted using Chi-square of Fisher's Exact Test.

### ***6.1.2 Sensitivity Analyses for the Primary Efficacy Variable***

The NRI analysis of EASI-50, as well as EASI-75 and EASI-90, will be repeated using a logistic regression model with fixed effects for treatment and country. Odds ratio estimates and the Wald 95% confidence intervals will be provided for the pairwise comparisons of baricitinib to placebo.

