### 6.1 Primary Efficacy Analysis

The primary efficacy analysis will be based on the Eczema Area and Severity Index (EASI), which is a valid and internally consistent clinical observation tool that has adequate intra-observer reliability, intermediate inter-observer reliability, and adequate responsiveness.

The EASI assesses objective physician estimates of two dimensions of atopic dermatitis – disease extent and clinical signs – by scoring the extent of disease (percentage of skin affected: 0 = 0%; 1 = 1-9%; 2 = 10-29%; 3 = 30-49%; 4 = 50-69%; 5 = 70-89%; 6 = 90-100%) and the severity of four clinical signs (erythema, induration/papulation, excoriation, and lichenification) each on a scale of 0 to 3 (0 = none, absent; 1 = mild; 2 = moderate; 3 = severe) at four body sites (head and neck, trunk, upper limbs, and lower limbs). Half scores are allowed. Each body site will have a score that ranges from 0 to 72, and the final EASI score will be obtained by weight-

averaging these four scores (using multipliers 0.2 for head and neck and upper limbs and 0.3 for trunk and lower limbs). Hence, the final EASI score will range from 0 to 72 for each time point.

The EASI will be assessed at baseline and at Weeks 1, 4, 8, 12, and 16 post-randomization, plus at the early termination visit, if applicable. At each of the post-baseline visits the EASI will be computed, and the EASI score will be compared with the EASI score obtained at baseline to obtain the proportion of reduction.

The primary efficacy measure will be the proportion of moderate-to-severe atopic dermatitis patients achieving a 50% reduction in the Eczema Area and Severity Index, or EASI-50, after 16 weeks of treatment. The primary analysis will be performed using a Non-Responder Imputation (NRI) analysis. All patients with a less than 50% reduction in the EASI at Week 16, plus all patients who either discontinue study treatment or discontinue from the study for any reason at any time prior to Week 16 will be defined as non-responders for the NRI analysis. Randomized patients without at least 1 post-baseline observation of EASI will also be defined as non-responders for the NRI analysis.

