The proportion of patients achieving EASI-50 in the placebo arm will be compared to the proportion of patients in each of the baricitinib arms (2 mg and 4 mg) using a two-sided chi-square test with  $\alpha=0.05$ . To control for multiplicity testing will be performed in a stepwise fashion. First, the 4-mg baricitinib arm will be compared with the placebo arm; if this test is statistically significant, then the 2-mg baricitinib arm will be compared with the placebo arm.

The number and percent of patients, based on an NRI analysis, with a 50% reduction in EASI will be presented for each treatment arm at each time point including the patient's last assessment, which should be either Week 16 or the early termination visit. The p-values for the pairwise chi-square tests from the NRI analyses will also be tabulated. In addition, a bar chart that shows the percentage of patients with a 50% reduction in EASI for each treatment arm at each time point including the patient's last assessment will be presented. The figure displays will be generated for the overall population and by country – United States and Japan.

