## 6.2 Secondary Efficacy Analyses

### 6.2.1 *Change and Percentage Change in EASI*

Change and percentage change from baseline for EASI will be derived for each patient at each post-baseline visit (Weeks 1, 4, 8, 12, and 16). Descriptive statistics for the value, change and percentage change will be tabulated for each time point.

Missing assessments will assumed to be missing at random and separate mixed effects model repeated measures (MMRM) analyses will be performed to compare the baricitinib treatment arms and placebo for the actual and percent change from baseline. For both change and percent change from baseline the MMRM model will contain fixed effects for treatment, visit, and country and the treatment-by-visit interaction plus the baseline value and baseline-by-visit term as covariates. Patient will be nested within treatment, and the covariance structure among the repeated measurements for a patient will be assumed to be common across patients and modeled using an unstructured 5x5 matrix. Satterthwaite's approximation will be used to estimate denominator degrees of freedom. The significance of differences in least-square means will be based on Type III tests using the observed population margins. The analyses will be performed using the SAS procedure PROC MIXED.

The tabular output for these MMRM analyses will present the least squares means, standard errors and 95% confidence intervals and p-values for each main effect marginal. Pairwise contrasts of the least squares means between the randomized treatment arms will also be provided at each time point using LSMESTIMATE statements.

For both endpoints plots of the least squares mean  $\pm$  standard error estimates for changes in EASI over time will be provided by randomized treatment. These plots will be provided for the overall population and for each country.

Finally, a last observation analysis will be performed for both change and percent change using an analysis of covariance (ANCOVA) model with fixed effects for treatment and country plus the baseline value as a covariate. Tabular output for these ANCOVA analyses will present the least squares means, standard errors and 90% confidence intervals and p-values for each main effect marginal. Pairwise contrasts of the least squares means will also be provided for randomized treatment arms at each time point.

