### ***6.3.4 Exploratory Subgroup Assessment of Response***

Subgroup assessments of response based on patient and disease characteristics will be performed on an ad hoc basis. Reviews of the data will include evaluations of potential prognostic and predictive disease characteristics with specific interest in how these prognostic factors impact the EASI score. If a potential prognostic factor merits further consideration the exploratory analyses will at least include an NRI logistic regression analysis of the EASI-50 after 16 weeks where treatment, country and the potential factor are included in the model.

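### The only prespecified interval estimate for EASI-50 is not adjusted for baseline EASI, although the continuous EASI models are: a minor, one-term improvement

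*SAP*

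**What the plan says.** The primary comparison of EASI-50 at Week 16 is made "using a two-sided chi-square test with" a 5% level, with no covariates (SAP Section 6.1). The endpoint is relative to each patient's own starting value: "the EASI score will be compared with the EASI score obtained at baseline to obtain the proportion of reduction".

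The sensitivity analysis in Section 6.1.2 "will be repeated using a logistic regression model with fixed effects for treatment and country". Its output is: "Odds ratio estimates and the Wald 95% confidence intervals will be provided for the pairwise comparisons of baricitinib to placebo". Section 6.1 itself promises counts, percentages and p-values, and Section 6.1.1 adds further tests. Neither gives an effect estimate with an interval.

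The models for the same scale in Section 6.2.1 do use baseline, for change and for percentage change alike. The MMRM includes "the treatment-by-visit interaction plus the baseline value and baseline-by-visit term as covariates". The last-observation ANCOVA is specified "with fixed effects for treatment and country plus the baseline value as a covariate".

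Section 6.3.4 provides for a further logistic model of EASI-50, ad hoc, "where treatment, country and the potential factor are included in the model". Baseline EASI enters it only if someone picks it as the factor.

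**The concern.** Percentage change in EASI is the quantity that EASI-50 cuts at 50%. The plan adjusts that quantity for baseline when it is analysed as a continuous variable and drops the adjustment once it is dichotomised. It gives no reason.

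The omission matters because of where it falls. Section 6.1.2 is the only prespecified model of the primary endpoint and the only source of an interval for it. Randomization is stratified by country alone (Section 2.4), so nothing in the design balances severity. If the arms differ in baseline EASI, a reader will ask whether the EASI-50 result depends on that difference, and the planned sensitivity analysis cannot answer. Section 1.1 allows supportive analyses to be added later without amendment, and Section 2.1 allows a small sponsor team to see unblinded data before the trial ends. A covariate named now is more credible than one chosen later.

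**Working it through.** **Inputs from the SAP.** About 120 patients at 4:3:3 gives 48 on placebo and 36 on each dose (Section 1.3). All randomized patients count under non-responder imputation (Section 2.3), so 48 v 36 applies. The design difference is 35 points at 90% power (Section 1.3).

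**Assumptions.** The SAP gives neither the placebo rate nor the prognostic strength of baseline EASI. The main scenario is 30% v 65%. Prognostic strength is varied.

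**Step 1: reproduce the stated power.** For 30% v 65%, the pooled rate is (48 × 0.30 + 36 × 0.65)/84 = 0.45.
- Null SE = √[0.45 × 0.55 × (1/48 + 1/36)] = 0.1097
- Alternative SE = √(0.30 × 0.70/48 + 0.65 × 0.35/36) = 0.1034
- z = (0.35 − 1.96 × 0.1097)/0.1034 = 1.31, so power is 0.904

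Placebo rates of 25% to 40% give 0.903 to 0.911. The stated 90% is reproduced, and the scenario fits the plan.

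**Step 2: size of a chance imbalance.** The SD of the difference in mean standardised baseline is √(1/48 + 1/36) = 0.22. The shift in the log odds ratio is about slope × imbalance. The design log odds ratio is ln(0.65/0.35) − ln(0.30/0.70) = 1.47.

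| Assumed slope per SD | Shift at a 1-SD imbalance (0.22) | In points near 50% response (× 0.25) | Shift at a 1.96-SD imbalance (0.43) | Share of 1.47 |
|---|---|---|---|---|
| 0.3 | 0.07 | 1.7 | 0.13 | 9% |
| 0.5 | 0.11 | 2.8 | 0.22 | 15% |
| 0.8 | 0.18 | 4.4 | 0.35 | 24% |

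**Step 3: what adjustment does.** Logistic models with treatment and country were simulated with and without standardised baseline EASI: 48/36/36 patients, 5,000 trials per row, 30% v 65% for placebo v 4 mg. Further assumptions were 50% response on 2 mg, a 35/65 country split and no country effect. Each cell reads without → with baseline.

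| Odds ratio per SD (slope = ln) | Mean log odds ratio | Mean SE of log odds ratio | Wald power | SD of standardised risk difference |
|---|---|---|---|---|
| 1 (0) | 1.535 → 1.550 | 0.486 → 0.491 | 90.6 → 90.7% | 0.1036 → 0.1041 |
| 1.25 (0.22) | 1.533 → 1.564 | 0.485 → 0.494 | 90.5 → 90.7% | 0.1028 → 0.1025 |
| 1.5 (0.41) | 1.528 → 1.601 | 0.485 → 0.503 | 89.9 → 90.4% | 0.1055 → 0.1045 |
| 2 (0.69) | 1.533 → 1.713 | 0.485 → 0.524 | 90.3 → 92.4% | 0.1037 → 0.0990 |
| 3 (1.10) | 1.525 → 1.924 | 0.485 → 0.569 | 89.2 → 94.5% | 0.1045 → 0.0951 |

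The SE of the log odds ratio rose in 99% to 100% of trials. At an odds ratio of 2 per SD it rose by 0.524/0.485 − 1 = 8%. Power still rises because the estimate moves further than its SE: 1.533/0.485 = 3.16 becomes 1.713/0.524 = 3.27. On the risk-difference scale the spread falls visibly only in the last two rows.

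A separate simulation at the slopes used in Step 2, again at 30% v 65%, gave power of 90.3 → 90.7% (0.3), 90.0 → 90.8% (0.5) and 90.0 → 93.0% (0.8).

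**The case against.** **The primary test does not need this.** Under randomization the unadjusted chi-square test is valid, and the unadjusted interval already allows for chance imbalance on average. That stands. The remaining question is what a particular imbalance did in the trial as it turned out.

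**EASI-50 is already normalised to baseline.** Absolute change depends on baseline almost by construction; proportional response need not. The SAP gives no figure, so the slope is an assumption. That stands, and it limits the claim about power. It does not explain why percentage change, normalised in the same way, is adjusted in Section 6.2.1.

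**The plan is consistent in its own way.** The responder comparisons for IGA, DLQI and itch are also made without baseline adjustment, and the logistic model serves to bring in the stratifier, country. So this is not an internal contradiction.

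**Other routes exist.** Section 6.3.4 could take baseline EASI as its factor, but only ad hoc. The MMRM of percentage change is adjusted and has 95% intervals, but it assumes data missing at random instead of imputing non-response, so it does not check the primary endpoint as defined.

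**Another term may strain EASI-75 and EASI-90.** Section 6.1.1 expects low response rates there. That stands, and the fix needs a safeguard.

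**A stronger reading.** A reader might infer that leaving baseline out makes the reported odds ratio less precise, as it would in a linear model. It does not. In a logistic model, adjustment moves the estimate to a larger conditional odds ratio with a larger SE, as the simulation shows.

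**Conclusion.** The point holds as a minor improvement to a sensitivity analysis. The omission is plain in the text, has no stated reason, and sits in the only prespecified interval estimate for EASI-50.

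The firmest gain is robustness: an imbalance with SD 0.22 would no longer go unadjusted. The gain in power is about 0 to 1 point at slopes of 0.3 to 0.5 and about 3 points at 0.8. Risk-difference precision improves only if baseline is strongly prognostic. If baseline does not predict response, there is nothing to gain and almost nothing to lose.

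These sizes rest on an assumed placebo rate of 30% and on assumed slopes. With 20% v 55% the pattern is the same. The documents do not support a claim that the primary analysis is biased or wrong.

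**What to change.** - In Section 6.1.2, fit treatment, country and continuous baseline EASI for EASI-50. Make baseline EASI a standing term in the Section 6.3.4 model too.
- State that the odds ratio is conditional on baseline EASI. Alternatively, report a standardised risk difference with an interval: average the model's predicted response over all patients under each treatment, and take the difference.
- For EASI-75 and EASI-90, add the same term with a sparse-data method such as Firth penalisation when responders are few. Fix in advance what counts as few.
- Leave the primary chi-square test and the stepwise order of doses as they are.

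The cost is one term in two models and one table footnote. No new data are needed, because EASI-50 cannot be derived without baseline EASI. No further patients are lost either, since Section 6 already excludes those without a baseline value from the analysis of that variable. The downside is a slightly wider odds-ratio interval, for example an SE of 0.524 instead of 0.485 at an odds ratio of 2 per SD.

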## 6.2 Secondary Efficacy Analyses

### 6.2.1 *Change and Percentage Change in EASI*

Change and percentage change from baseline for EASI will be derived for each patient at each post-baseline visit (Weeks 1, 4, 8, 12, and 16). Descriptive statistics for the value, change and percentage change will be tabulated for each time point.

Missing assessments will assumed to be missing at random and separate mixed effects model repeated measures (MMRM) analyses will be performed to compare the baricitinib treatment arms and placebo for the actual and percent change from baseline. For both change and percent change from baseline the MMRM model will contain fixed effects for treatment, visit, and country and the treatment-by-visit interaction plus the baseline value and baseline-by-visit term as covariates. Patient will be nested within treatment, and the covariance structure among the repeated measurements for a patient will be assumed to be common across patients and modeled using an unstructured 5x5 matrix. Satterthwaite's approximation will be used to estimate denominator degrees of freedom. The significance of differences in least-square means will be based on Type III tests using the observed population margins. The analyses will be performed using the SAS procedure PROC MIXED.

The tabular output for these MMRM analyses will present the least squares means, standard errors and 95% confidence intervals and p-values for each main effect marginal. Pairwise contrasts of the least squares means between the randomized treatment arms will also be provided at each time point using LSMESTIMATE statements.

For both endpoints plots of the least squares mean  $\pm$  standard error estimates for changes in EASI over time will be provided by randomized treatment. These plots will be provided for the overall population and for each country.

Finally, a last observation analysis will be performed for both change and percent change using an analysis of covariance (ANCOVA) model with fixed effects for treatment and country plus the baseline value as a covariate. Tabular output for these ANCOVA analyses will present the least squares means, standard errors and 90% confidence intervals and p-values for each main effect marginal. Pairwise contrasts of the least squares means will also be provided for randomized treatment arms at each time point.

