## **2.9 Changes to the Planned Analyses**

### ***2.9.1 Changes to the Planned Analyses in the Protocol***

- There was a typo for the analyses of continuous secondary efficacy endpoints. The level for the confidence intervals should have been 95%, rather than 90%. The correction has been implemented in this SAP.

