### 6.2.2 *SCORing Atopic Dermatitis (SCORAD)*

To determine disease severity the SCORing Atopic Dermatitis (SCORAD) index uses the rule of nines to assess disease extent (head and neck 9%; upper limbs 9% each; lower limbs 18% each; anterior trunk 18%; back 18%; genitals 1%; and hands 2%) and evaluates six clinical characteristics – erythema, edema/papulation, oozing/crusts, excoriation, lichenification and dryness – each on a scale of 0 to 3 (0 = none, absent; 1 = mild; 2 = moderate; 3 = severe). SCORAD also assesses subjective symptoms of pruritus and sleep loss with visual analogue scales (VAS) where 0 is no itch (or no sleeplessness) and 10 is the worst imaginable itch (or sleeplessness). These three aspects: extent of disease (A: range 0-102), disease severity (B; range 0-18) and subjective symptoms (C: range 0-20) will be combined using,  $A/5 + 7*B/2 + C$ , to give a maximum possible score of 103.4.

The SCORAD will be assessed at baseline and at Weeks 1, 4, 8, 12, and 16 post-randomization, plus at the early termination visit, if applicable. At each of the post-baseline visits the SCORAD will be computed, and the SCORAD score will be compared with the SCORAD score obtained at baseline to obtain change and percent change from baseline. Descriptive statistics for the SCORAD value and the subjective assessments of pruritus and sleep loss and the respective changes from baseline will be tabulated for each time point using the overall and by-country populations.

The MMRM and ANCOVA analyses described in [Section 6.2.1](#) will be performed to compare the baricitinib treatment arms and placebo for change and percent change from baseline in the SCORAD score, and change from baseline in the pruritus and insomnia assessments. The tabular outputs for the MMRM and ANCOVA analyses described will be provided.

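### The SAP says the 90% confidence level was corrected to 95%, but the ANCOVA output in Section 6.2.1 still specifies 90%, and four other instruments inherit it

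*SAP*

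**What the plan says.** Section 2.9.1 lists a single change from the protocol's planned analyses. It opens "There was a typo for the analyses of continuous secondary efficacy endpoints" and continues "The level for the confidence intervals should have been 95%, rather than 90%. The correction has been implemented in this SAP".

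Section 6.2.1 then sets out two analyses of change and percent change in EASI:

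- **MMRM:** "The tabular output for these MMRM analyses will present the least squares means, standard errors and 95% confidence intervals and p-values".
- **Last-observation ANCOVA**, at the end of the section: "Tabular output for these ANCOVA analyses will present the least squares means, standard errors and 90% confidence intervals and p-values".

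In both sentences the interval belongs to the least squares means for the main effects. Each paragraph then adds pairwise contrasts between arms, with no confidence level given for them.

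Four later sections use the Section 6.2.1 MMRM and ANCOVA by cross-reference and state no level of their own: 6.2.2 (SCORAD, including pruritus and insomnia), 6.2.4 (DLQI), 6.2.5 (Itch NRS) and 6.3.1 (POEM). Section 6.2.2, for example, adds "The tabular outputs for the MMRM and ANCOVA analyses described will be provided". Sections 6.2.5 and 6.3.1 say much the same. Section 6.2.4 calls for the analyses without repeating the remark about tables.

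**The concern.** Two operative statements of the same SAP disagree. Section 2.9.1 describes the protocol's level as superseded, but it also says what this SAP now does, and for the ANCOVA that statement is not true. A programmer who works from Section 6.2.1 produces 90% intervals; one who works from Section 2.9.1 produces 95%. The independent programming promised in Section 2 need not expose this, because both programmers may work from 6.2.1.

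Two things are at stake. First, MMRM and ANCOVA results for one endpoint would be tabulated at different levels, and the ANCOVA would look more precise only because of the level. Second, the SAP tests at a two-sided 0.05 wherever it names a level. A 90% interval can exclude zero when the p-value beside it is above 0.05, so one table could point two ways.

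**Working it through.** The level is a prescription, so there is no figure of the plan's to reproduce. The check has three parts.

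**1. The level in each place**

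| SAP section | Analysis | Level |
|---|---|---|
| 2.9.1 | Continuous secondary endpoints | 95%, replacing 90% |
| 6.1.2 | Logistic sensitivity analysis of EASI-50, -75 and -90 | 95% |
| 6.2.1 | MMRM, EASI change and percent change | 95% |
| 6.2.1 | ANCOVA, EASI change and percent change | **90%** |
| 6.2.2, 6.2.4, 6.2.5, 6.3.1 | ANCOVA by reference to 6.2.1 | none stated, so 90% inherited |

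Table JAHG.1 lists absolute and percent change in EASI as a secondary objective, so the ANCOVA is within the scope of 2.9.1. Nothing in the SAP gives a reason for a different level in the ANCOVA.

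**2. Effect on width**

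At a fixed standard error, the half-width is the critical value times the standard error. The ratio of 90% to 95% widths is therefore the ratio of critical values.

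- Normal: 1.6449 / 1.9600 = 0.839, so the 90% interval is 1 − 0.839 = 16.1% narrower. Conversely, the 95% interval is 1.9600 / 1.6449 − 1 = 19.2% wider.
- t distribution: Section 1.3 gives about 120 patients enrolled and about 96 completing. The ANCOVA has 5 parameters (intercept, 2 for treatment, 1 for country, 1 for baseline), so the error degrees of freedom are 120 − 5 = 115 or 96 − 5 = 91.
  - df 115: 1.6582 / 1.9808 = 0.837, 16.3% narrower.
  - df 91: 1.6618 / 1.9864 = 0.837, 16.3% narrower.
- Small subsets: Section 6 also plans many reports for patients in Japan alone, and Section 2.4 does not fix their number. Taking df 25 and df 10 as illustrative assumptions, the shortfall is 17.1% and 18.7%.

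Nominal non-coverage is 1 − 0.90 = 10%, against 1 − 0.95 = 5%.

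**3. Agreement with the p-value**

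A two-sided 90% interval excludes zero when the absolute ratio of estimate to standard error exceeds 1.645 (p < 0.10). A 95% interval needs 1.960 (p < 0.05). For any estimate with 0.05 < p < 0.10, the 90% interval excludes zero and the 95% interval does not. In the 6.2.1 wording this applies to the least squares means. It applies to baricitinib-versus-placebo contrasts if the same level is carried over to them.

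**The case against.** The strongest reply is that this is a missed edit of little consequence. The intended level is on record in 2.9.1, and no decision rule in the SAP uses these intervals. The ANCOVA follows an MMRM that already has 95%. A 90% interval labelled as such is correctly calculated, and a reader could convert it using the tabulated standard error. All of this is fair. It limits the importance of the point but does not remove the contradiction, because 6.2.1 is the instruction that programmers implement. The interval is too narrow only relative to the level the SAP says it uses.

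Some narrower points also stand:

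- The 90% is attached to the least squares means. Since the contrasts have no stated level, a conflict between interval and p-value for a treatment difference is a risk and does not follow directly from the text.
- POEM is exploratory and outside the literal scope of 2.9.1. It receives the 90% only by cross-reference.
- For DLQI the ANCOVA is required, but the tabular output is not explicitly repeated.
- The table formats are in a companion document that is not at hand, so whether they also carry 90% is unknown.

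**Conclusion.** The concern holds. Section 6.2.1 specifies 90% for the ANCOVA although Section 2.9.1 gives 95% as the right level and reports it as implemented. Followed as written, the ANCOVA intervals for EASI come out about 16% narrower than the SAP's stated standard (16.1% normal, 16.3% with t at df 91 or 115), and so do those for SCORAD, DLQI, Itch NRS and POEM by cross-reference. These figures assume that the standard error is unchanged and that programmers follow 6.2.1 over 2.9.1.

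Point estimates, standard errors and p-values do not change, and the primary EASI-50 comparison is untouched. This is a reporting inconsistency in secondary and exploratory results. It should be corrected before the tables are programmed, but it does not threaten the trial's main conclusion.

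**What to change.** - In the ANCOVA paragraph of Section 6.2.1, replace 90% with 95%. This makes the statement in 2.9.1 true and corrects the four sections that refer back.
- In the same edit, state 95% for the pairwise contrasts in both the MMRM and ANCOVA paragraphs, where no level is given now.
- Check the companion table formats and the ANCOVA program for a leftover 90% setting.

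The cost is one number and a short clause in the SAP, plus one option in the ANCOVA program. No data, sample size or test is affected.
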